#### 1 Medical device for surveillance

Category	Instrument and Apparatus(07)Visceral Function Substitute Device
Generic name	Stent graft with heparin for central circular system (Vascular stent graft with heparin)
Brand name	GORE® VIABAHN® stent graft

#### 2 Purpose

To confirm the efficacy and safety in the clinical setting after the launch of the GORE® VIABAHN® stent graft (hereafter referred to as "Viabahn") for the treatment of patients with stenosis or occlusion at the venous anastomosis of synthetic arteriovenous access graft

#### 3 Target number of cases and rationale for setting

Target number of cases : 100 cases (indicated cases)

Rationale :

[REDACTED]

#### 4 Target patients

Patients who developed stenosis or occlusion at the venous anastomosis of synthetic arteriovenous access graft (indicated cases) will be target patients. In addition, patients

who was used to repair vascular access circuits for purposes other than treatment of stenosis or occlusion at the venous anastomosis of synthetic arteriovenous access graft will be also enrolled in this surveillance and this surveillance will be conducted in conjunction with the indicated cases.

## 5 Planned sites

After the start of this surveillance, the sites which concluded a contract based on the standards for Good Post-marketing Study Practice (hereafter referred to as "GPSP ordinances") and used Viabahn, and in addition to that, the sites which have physicians determined to be able to use Viabahn properly will be the planned sites. The number of sites by departments where this surveillance may be conducted is as follows. During this surveillance, the number of sites may vary depending on the enrollment status.

Clinical departments	Planned number of sites
Urology	1
Nephrology	6
Cardiology	1
Surgery	3
Dialysis	1
Vascular surgery	1

In this surveillance, it is important to collect treatment results by physicians in clinical departments performing dialysis who have not previously used Viabahn, and assess the sufficiency of the post-marketing safety measures. Therefore, sites should be chosen so that patients are enrolled in a fixed number even in clinical departments where dialysis is performed.

The AVR 06-01 study conducted in the United States was conducted at 31 sites, and 289 subjects were enrolled (143 in Viabahn group and 146 in PTA group).

## 6 Method of surveillance

This surveillance complies with Act on Securing Quality, Efficacy and Safety of Products Including Pharmaceuticals and Medical Devices and GPSP ordinances and uses Electronic Data Capture systems (hereafter referred to as "EDC") to collect information on cases who used Viabahn after concluding a contract in the sites.

This surveillance will be conducted with a consecutive surveillance system in which patients who used Viabahn are enrolled consecutively in this surveillance. Inclusion, enrollment, data bases for analysis will be prepared according to the following procedures.

- (1) Enrollment should be performed after fully explaining the purpose and plan of this surveillance and concluding a contract with sites for this surveillance. Enrollment is completed by providing case information on the Case Registration Form from site staff to the contract research organization (hereafter referred to as "CRO") and receiving it by CRO.
- (2) After obtaining the information on the Case Registration Form, the CRO will make the data of the case available for entry into the EDC. The enrollment of the case will be completed by the fact that data can be entered into the EDC.
- (3) When EDC becomes available for entry, investigator is asked to enter the surveillance information into the EDC, and the investigator or site staff enter the information into the EDC.
- (4) Using the information entered in EDC, create a database for analysis.

## **7 Planned surveillance period**

Total surveillance period : 4 years after obtaining approval

Preparation period : about 8 months

Enrollment period : about 6 months

Follow-up period : 24 months from procedure

Supplemental surveillance period, data fixed period, analysis period : about 10 months

## **8 Surveillance items, etc**

### **8.1 Surveillance items**

This surveillance collects following items. No focused survey items will be established in this surveillance.

#### **(1) Treatment**

- Patient information
  - Age, sex, height, weight, smoking history, family history of myocardial infarction, treatment history of ischemic heart disease, etc.
- Medical history
  - Myocardial infarction, transient ischemic attack, etc.
- Primary disease / Complication

- Primary disease : diabetic nephropathy, chronic glomerulonephritis, nephrosclerosis, polycystic kidney disease, chronic pyelonephritis, interstitial nephritis, rapidly progressive glomerulonephritis, nephritis associated with autoimmune diseases, etc.
- Complication : dyslipidemia, hypertension, diabetes mellitus, metabolic syndrome, heart failure, peripheral arterial disease, stroke, etc.
- Pre-procedure information
  - Echocardiography, electrocardiography, assessment of cardiac function, laboratory data (BNP, etc.), etc.
- Characteristics of lesion
  - Location of the lesion, palpation, auscultation, etc.
- Secondary lesion information in the vascular access circuit after the procedure
- Procedure information at the time of treatment
  - Procedure time, blood flow before and after the procedure, vein pressure, etc.
- Information on Viabahn
  - Item and Lot Number
- Other device information used during treatment

(2) Follow-up information

- Information on vascular access and Viabahn
- Information on dialysis treatment continuation
- Information on discontinuation

(3) Failure

- Name of failure, date of occurrence, etc.

(4) Adverse events

- Name of adverse event, date of onset, severity, causal relationship, etc.

(5) Re-treatment

- Information on vascular access and lesions
  - Blood flow and venous pressure before and after re-treatment, palpation,

---

 Lesions not treated with Viabahn at the treatment

 Refers to the blood flow through the entire shunt.

 Refers to static venous pressure (sVP) or dynamic venous pressure (dVP). The venous pressure should be measured by the same method before and after the initial placement and before and after re-treatment of each patient.

auscultation, etc.

- Information on re-treatment
  - Performed treatment, clinical indications, etc.
- Other device information used during re-treatment

(6) Concomitant drugs (antiplatelet drugs, etc.)

- Drug Name
- Date of first administration
- Date of completion of administration

## 8.2 Planned surveillance items at each visit

This surveillance will collect surveillance information at treatment, 1 month, 3 months, 6 months, 12 months, and 24 months. Planned surveillance items at each visit are as follows:

**Table1** Planned surveillance items at each visit

	treatment	1 month	3 months	6 months	12 months	24 months
Patient information	X					
Medical history	X					
Primary disease/Complication	X					
Pre-procedure information	X					
Characteristics of lesion	X					
Secondary lesion information in the vascular access circuit after the procedure (the lesion not treated with Viabahn)		X				
Procedure information at the time of treatment	X					
Information on Viabahn	X					
Other device information used during re-treatment	X					
Follow-up information		X	X	X	X	X
Adverse events and failure						
Re-treatment						
Concomitant drugs (Antiplatelet drugs, etc.)						

X: Input

### 8.3 Desired visit period

The desired visit period is as follows.

**Table2 Desired visit period**

Follow-up visit	Desirable visit period (days)
treatment	0
1 month	15 – 45
3 month	60 – 120
6 month	120 – 240
12 month	275 – 455
24 month	640 – 820

## 9 Items and methods for analysis

The following effectiveness and safety items will be evaluated.

### 9.1 Effectiveness endpoint

#### (1) Primary patency of target lesion

Primary patency of target lesion is defined as the period during the patency was maintained from initial treatment until occlusion of target lesion or re-treatment of target lesion. Primary patency of target lesions is calculated by Kaplan-Meier method.

#### (2) Secondary patency of target lesion

Secondary patency of target lesion is defined as the period during the patency was maintained from initial treatment (including the period of patency after re-treatment). Secondary patency of target lesions is calculated by Kaplan-Meier method.

#### (3) Primary patency of vascular access circuit

Primary patency of vascular access circuit is defined as the period during the patency was maintained from initial treatment until occlusion in vascular access or re-treatment in vascular access circuit. Primary patency of vascular access circuit is calculated by Kaplan-Meier method.

---

 Occlusion lesions occurring in Viabahn or within 5mm from the periphery or center of Viabahn

 Intervention for lesions (occlusion or stenosis) occurring in Viabahn or within 5mm from the periphery or center of Viabahn

(4) Secondary patency of vascular access circuit

Secondary patency of vascular access circuit is defined as the period during the patency was maintained from initial treatment until discontinuation of the use of vascular access circuit. Secondary patency of vascular access circuit is calculated by Kaplan-Meier method.

(5) Mean cumulative number of re-treatment in target lesion

Mean cumulative number of re-treatment in target lesion is defined as the number of re-treatment performed for target lesion after the initial treatment.

(6) Technical Success

Technical Success is defined as < 30% residual stenosis after initial treatment.

The residual stenosis should be calculated as follows.

$$\% \text{ stenosis} = \frac{(\text{reference diameter} - \text{stenosis diameter})}{\text{reference diameter}} \times 100$$

The definition of stenosis diameter and reference diameter is as follows.

Stenosis diameter: Diameter of the thinnest part after deployment of Viabahn

Reference diameter: Diameter of the non-stenosis part in the vicinity of the stenosis

(7) Clinical Success

Clinical Success is defined as the resumption of normal dialysis for at least one session after the initial treatment.

## 9.2 Safety endpoint

- (1) Incidence of device and procedure-related adverse events at treatment and up to 30 days after treatment.
- (2) Incidence of adverse events and device defect in each follow-up period

The definitions of adverse events and failures in this surveillance are as follows.

**Table3 Adverse events and failures in this surveillance**

Adverse events	Any unfavorable or unintended sign (including abnormal laboratory changes), symptom, or illness associated with the use of a medical device. Unless worsening of severity or increasing of incidence during the surveillance, the primary disease of the patient is not considered an adverse event.
Device Defect	Defects such as damage, malfunction, etc. that are widely unfavorable. Regardless of whether they are due to design, marketing, distribution, or use. Medical device failures include the following: 

(1) Specification issues

(2) Defective product

(3) Malfunction or damage

(4) Insufficient description of package inserts, etc.

(5) Device-related adverse events

Serious adverse events are defined as any of the following adverse events.

- (1) Death
- (2) Disability
- (3) Cases that may lead to death
- (4) Cases that may lead to disability
- (5) Requires hospitalization or prolongs an existing hospitalization
- (6) Serious according to the cases listed in (1)~(5) above
- (7) Any congenital disease or anomaly in the offspring of treated patient.

The term "hospitalization" in (5) does not include hospitalization (scheduled surgery, examination, etc.) intended only to carry out the scheduled therapy or examination before the surveillance during the surveillance period (however, any newly occurring during that hospitalization should be handled as an adverse event).

### **9.2.1 Collection period for adverse events and device defect**

From the time of treatment to the end of the surveillance (24 months or discontinuation of the study). The time of treatment with Viabahn should be the time of initial treatment.

### **9.2.2 Evaluation of the causal relationship for adverse events**

The causal relationship between the adverse event and surveillance device (Viabahn placed at the initial treatment) and procedure at initial treatment (placement of surveillance device) will be determined according to the table below, taking into account the condition of the patient, complications, medical history, and time-to-onset relationship. When necessary, the rationale for causal relationship assessment should be entered into the EDC.

**Table4 Evaluation of the causal relationship for adverse events**

Causal relationship	Criteria
No related to device or procedure	The surveillance device and procedure at initial treatment are not considered to be related to the adverse event.
Device-related	The surveillance device are considered to be related to the adverse event that occurred after the procedure at the initial treatment,
Procedure-related during placement of surveillance device	The procedure at the initial treatment is considered to be related to the adverse event
Unknown	The causal relationship between the surveillance device and the adverse event cannot be undeniable.

### **9.2.3 Evaluation of the outcome for adverse events**

The outcome of adverse events will be assessed according to the table below.

**Table5 Evaluation of the outcome for adverse events**

Outcomes	Criteria
Recovery	In the case of disappearance / recovery of the adverse event and the adverse event related to laboratory values, normalization or recovery to values before placement level of the surveillance device
Remission	Reduced degree of the adverse event or with a tendency to improve
Not recovered	Little change in the extent of the adverse event or those with exacerbation
Death	Mortalities associated with the adverse event
Unknown	Undertaken the follow-up of the adverse event but have not been able to follow the outcome

## **10 Organizational structure for surveillance**

Same as the basic plan for post-marketing surveillance.

## **12 Any other required information**

No other required information need to be recorded.

1.1 Position of Statistical Analysis Plan

This plan shows the statistical analysis plan of “Post-Marketing Study – Implantation of GORE® VIABAHN® for Treatment of patients with stenosis or occlusion at the venous anastomosis of synthetic arteriovenous (AV) access graft (hereinafter referred to as the “Study”).

1.2 Purpose of the Study

To confirm the efficacy and safety of GORE® VIABAHN® (hereinafter referred to as the “Device”) implanted in patients for the treatment of stenosis or occlusion at the venous anastomosis of synthetic arteriovenous (AV) access graft in the actual usage after approval.

■
2.1

2.2 Dictionary used

Dictionaries used for adverse events, complications and medical history are shown below.

Item	Name of Dictionary※	Note
Adverse event	MedDRA/J	
• SOC and PT are used for System Organ Class and Symptom Name, respectively• If SOC is shown, it is listed in order of the international agreement• If PT is shown, it is listed in order of PT code
Complications		
Medical History		

※The version used is the version used for coding. In principle, it is the latest version.

3. Definition of Abbreviations and Terms

3.1 Abbreviations

Abbreviation	Full description
MedDRA/J	Medical Dictionary for Regulatory Activities/Japanese version
SOC	System Organ Class。 System Organ Class in MedDRA/J
PT	Preferred Term。 Basic term in MedDRA/J

3.2 Safety endpoint

3.2.1 Adverse Event/ Device deficiency

Term	Definition
Adverse Event	Any undesirable or unintended signs (including abnormal laboratory results), symptoms, or diseases occurring related to the use of a medical device. A patient's primary disease is not considered an adverse event unless it aggravates in severity or increase in frequency during the study.
Device deficiency	A condition that is not good in a broad scope, such as fracture, malfunction, regardless of whether it is caused by design, manufacture, distribution, or use. Device deficiencies include: (1) Specification problem (2) Defective product (3) Malfunction/fracture (4) Insufficient description in the insert, etc. (5) Adverse events caused by the device
Serious Adverse Event	Serious adverse events are defined as any of the following among adverse events. (1) Death (2) Disability (3) May lead to death (4) May lead to disability (5) Requires hospitalization or prolonged hospitalization for treatment in a hospital or a clinic (6) Serious cases similar to those listed in (1) though (5) (7) Congenital disease or abnormality in future generations

Term	Definition
Unanticipated Device Deficiency/Adverse Event	Device deficiency and Adverse Event not described in the insert are classified as “Unanticipated Device deficiency/Adverse Event”.

3.2.1.1 Judgement of Causal relationship of Adverse Events

Causal relationship	Criteria for Judgement
Not related to the Device/ Procedures	In cases of no causal relationship between the investigational device/ index procedure and an adverse event
Related to the Device	In cases of a causal relationship between the investigational device and an adverse event among the adverse events occurring after index procedure
Related to Procedures at the time of implantation of the investigational device	In cases of a causal relationship between index procedure and an adverse event
Unknown	In cases of an undeniable causal relationship between the investigational device and an adverse event

3.2.2

3.2.3

[REDACTED]	[REDACTED]	[REDACTED]

3.3 Efficacy endpoints

[REDACTED]	[REDACTED]	[REDACTED]
[REDACTED]	[REDACTED]	[REDACTED]

Definition for each efficacy endpoint is as follows.

Primary Patency of target lesion	Period from index procedure until observation of occlusion in a target lesion or period of retention of patency until reintervention of a target lesion.
Secondary Patency of target lesion	Period from index procedure until retention of patency in a target lesion (including period of patency after reintervention)
Primary patency of vascular access	Period from index procedure until observation of occlusion in vascular access or period of retention of patency until reintervention in vascular access circuit.
Secondary patency of vascular access	Period that patency is maintained from index procedure until discontinuation of use of vascular access circuit.

3.3.1 Events of Primary Patency of Target Lesions and Termination

Primary patency of a target lesion is defined as the period after index procedure until reaching one of the following conditions at the earliest.

Event	EDC item	Date of Event
Occlusion of VIABAHN	Answer to “Did the device implanted in a treated lesion maintain patency? ([REDACTED]) ” is “Loss of patency ([REDACTED])	Date of follow-up ([REDACTED])

Event	EDC item	Date of Event
	Enter “Occlusion of VIABAHN” in “Adverse Event ([REDACTED])”	Date of onset ([REDACTED])
Conduct reintervention	“Purpose of reintervention ([REDACTED])” is “Patency of the initial implanted device ([REDACTED])”	Date of reintervention ([REDACTED])
Discontinuation of study	Answer to “Did conduct follow-up ([REDACTED])” is “Discontinuation ([REDACTED])” and “Reason for discontinuation ([REDACTED])” is “Other (discontinuation of use of the device, etc. ([REDACTED]))”	Date determined to be discontinued ([REDACTED])
	Answer to “Did complete the study? ([REDACTED])” is “Discontinuation ([REDACTED])” and “Reason for discontinuation ([REDACTED])” is “Other (discontinuation of use of the device, etc. ([REDACTED]))”	Date determined to be discontinued ([REDACTED])

In addition, termination is defined as the latest of the following dates.

Termination	EDC Item	Termination date
Completion of study	Answer to “Did complete the study? ([REDACTED])” is “Completed ([REDACTED])” and to “Did the device implanted in a treated lesion maintain patency? ([REDACTED])” is “Patency ([REDACTED])”	Date of completion ([REDACTED])
Study ongoing	Date of procedure [REDACTED]	Date of procedure [REDACTED]
	Answer to “Did the device implanted in a treated lesion maintain patency? ([REDACTED])” is “Patency ([REDACTED])”	Date of follow-up ([REDACTED])

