3.3.2 Events of Secondary patency of target lesions and termination

Secondary patency of a target lesion is defined as the period after index procedure until reaching one of the following conditions at the earliest. In the event “VIABAHN occlusion”, if the follow-up date for “Loss of Patency (██████████)” as the answer to the question “Did the device implanted in a treated lesion maintain patency? (██████████)” and onset date █████ or outcome date (██████████) of “recovered (██████████)” or “relived (██████████)” adverse event “Occlusion of VIABAHN” as the answer to “Outcome (██████████)” are the same, the event is not treated as an event.

Event	EDC Item	Event date
Occlusion of VIABAHN	
After answering “Loss of Patency (██████████)” to “Did the device implanted in a treated lesion maintain patency? (██████████)”, answer to the question “Did the device implanted in a treated lesion maintain patency? (██████████)” is not “Patency (██████████)” as well as “Recovered (██████████)” or “Relived (██████████)” adverse event “Occlusion of VIABAHN” is not entered in “Outcome (██████████)”. 
 
“Occlusion of VIABAHN” is entered in “Adverse event (██████████)” and “Outcome (██████████)” of adverse event “Occlusion of VIABAHN” is either “Unrecovered (██████████)” or “Death (██████████)” or “Unknown (██████████)”, and the answer to the subsequent question “Did the device implanted in a treated lesion maintain
	
Follow-up date of “Loss of Patency (██████████) (██████████) (██████████)”
 
Onset date (██████████)

Event	EDC Item	Event date
	patency? (██████████) ” is not “Patency (██████████) ████” as well as “Recovered (██████████) ” or “Relived (██████████) ” adverse event “Occlusion of VIABAHN” is not entered in “Outcome (██████████) ”.	
Discontinuation of study	Answer to “Did conduct follow-up (██████████) ” is “Discontinuation (F██████████) ” and “Reason for discontinuation (F██████████) ” is “Other (discontinuation of use of the device, etc. (██████████) ”	Date determined to be discontinued (██████████)
	Answer to “Did complete the study? (██████████) ” is “Discontinuation (██████████) ” and “Reason for discontinuation (██████████) ” is “Other (discontinuation of use of the device, etc. (██████████) ”	Date determined to be discontinued (██████████)

In addition, termination is defined as the latest of the following dates.

Termination	EDC Item	Termination date

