3.3.3 Events of primary patency of vascular access circuit and termination

Primary patency of vascular access circuit is defined as the period after index procedure until reaching one of the following conditions at the earliest. (If “Date of vascular access discontinuation” is entered, it is judged within the period up to the date of the discontinuation)

Evet	EDC Item	Date of Event
VIABAHN [REDACTED] Occlusion of VIABAHN	Answer to “Did the device implanted in a treated lesion maintain patency? [REDACTED])” is “Loss of patency [REDACTED]”	Date of follow-up ([REDACTED])
	[REDACTED] [REDACTED] “Occlusion of VIABAHN” is entered in “Adverse Event [REDACTED]”	Date of onset ([REDACTED])
Occlusion of vascular access	Answer to “Vascular access maintain patency? [REDACTED])” is Loss of patency [REDACTED]	Date of follow-up ([REDACTED])
	Enter “Occlusion of vascular access (Other than treated lesion)” in “Adverse Event [REDACTED]”	Date of onset ([REDACTED])
Conduct reintervention	“Purpose of reintervention [REDACTED])” is “Patency of the initial implanted device [REDACTED]” or “Patency of vascular access circuit (excluding a site of initial implantation of the device) [REDACTED]”	Date of reintervention ([REDACTED])
Discontinuation of study	Answer to “Did conduct follow-up [REDACTED])” is “Discontinuation [REDACTED]” and “Reason for discontinuation [REDACTED])” is “Other (discontinuation of use of the device, etc. [REDACTED])”	Date determined to be discontinued ([REDACTED])
	Answer to “Did complete the study? [REDACTED])” is “Discontinuation [REDACTED]” and “Reason for	Date determined to be discontinued ([REDACTED])

Evet	EDC Item	Date of Event
	discontinuation ([REDACTED])” is “Other (discontinuation of use of the device, etc. [REDACTED])”	
Discontinuation of vascular access	Answer to “Is vascular access used at the time of treatment continuously used? [REDACTED] ” is “No ([REDACTED])”	Date of discontinuation of vascular access used at the time of treatment [REDACTED]

In addition, termination is defined as the latest of the following dates.

Termination	EDC Item	Termination date
Completion of study	Answer to “Did complete the study? ([REDACTED])” is “Completed ([REDACTED])”, to “Did vascular access maintain patency? ([REDACTED])” is “Patency ([REDACTED])”, and to “Did the device implanted in the treated lesion maintain patency? ([REDACTED])” is “Patency ([REDACTED])”.	Date of completion [REDACTED]

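### Target-lesion patency in SAP 3.3.1 and 3.3.2 has no rule tied to the date the treated access is given up, so later answers about an unused device can decide the result

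*SAP*

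**What the plan says.** **Target lesion.** SAP 3.3.1 opens with "Primary patency of a target lesion is defined as the period after index procedure until reaching one of the following conditions at the earliest", and 3.3.2 with "Secondary patency of a target lesion is defined as the period after index procedure until reaching one of the following conditions at the earliest". The events in 3.3.1 are occlusion of the device, reintervention for patency of the device, and study discontinuation with the reason "Other (discontinuation of use of the device, etc". In 3.3.2 they are unreversed occlusion and the same discontinuation row. On censoring, 3.3.1 states: "In addition, termination is defined as the latest of the following dates". The dates listed include every follow-up visit at which the device is answered as patent. Neither section mentions whether the access is still in use.

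**Circuit.** SAP 3.3.3 adds that, where a date of access discontinuation is entered, "it is judged within the period up to the date of the discontinuation". SAP 3.3.4 has the same clause. Both sections also list giving up the access as a separate event, dated by the field "Date of discontinuation of vascular access used at the time of treatment".

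**Protocol.** Section 9.1(1) ends primary target-lesion patency at occlusion or re-treatment of that lesion and does not mention abandonment of the access. Section 9.2.1 sets the collection period for adverse events and device defects as "From the time of treatment to the end of the surveillance (24 months or discontinuation of the study"). The readable text does not say that giving up the access ends participation.

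**The concern.** The surveillance is meant to confirm efficacy and safety of the device in treating a dialysis access. Once the access is out of use, the state of the device reflects non-use and how the site answers the form, rather than the result of the treatment.

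The circuit clause has a purpose only if entries dated after abandonment can occur, and the circuit tables list study discontinuation and access discontinuation as separate rows. The SAP therefore provides for patients who give up the access but remain in follow-up. For those patients the circuit endpoints are protected and the target-lesion endpoints are not. One clinical situation can then yield opposite target-lesion results, depending on study status and on an answer about a graft no longer used.

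**Working it through.** **Text comparison**

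| | 3.3.1 / 3.3.2 (lesion) | 3.3.3 / 3.3.4 (circuit) |
|---|---|---|
| Assessment limited to the access-discontinuation date | No | Yes |
| Access discontinuation is an event | No | Yes |
| Study discontinuation coded 'Other' is an event | Yes | Yes |

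**One case followed through 3.3.1.** Suppose the access is given up on Day 200 with the device open and no earlier target-lesion event.

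- The patient leaves the study under 'Other': failure on the date determined to be discontinued.
- The patient stays and the site answers 'Loss of patency' at 12 months: failure at that visit. Under 3.3.2 it is also a secondary event if never reversed.
- The patient stays and the site answers 'Patency' through to completion: censored as patent at completion, about Day 730.
- The patient stays and the device question is left blank: censored at the last visit answered 'Patency', since SAP 4.2.1 imputes nothing.

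A patient whose lesion occluded or was re-treated before abandonment is unaffected for primary patency, because that event is already counted.

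**Size.** The readable documents give no patency or abandonment rate, so there is no figure of the plan to reproduce and every input here is assumed. Let L and A be constant, independent hazards of target-lesion loss and of abandonment, and let t be 24 months. All patients who abandon the access stay in the study.

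- Censored at abandonment: exp(−Lt)
- All abandoned devices recorded lost: exp(−(L+A)t)
- All recorded patent: 1 − [L/(L+A)] × [1 − exp(−(L+A)t)]
- Proportion abandoned with the device open: [A/(L+A)] × [1 − exp(−(L+A)t)]

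With 50% true patency, Lt = −ln(0.5) = 0.693. For 10% abandonment, At = −ln(0.9) = 0.105. Then:

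- all lost: 0.5 × 0.9 = 45.0%
- all patent: 1 − (0.693/0.799) × 0.55 = 52.3%
- abandoned with device open: (0.105/0.799) × 0.55 = 7.3%

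| 24-month abandonment | Abandoned, device open (per 100) | Censored | All recorded lost | All recorded patent |
|---|---|---|---|---|
| 5% | 3.6 | 50% | 47.5% | 51.1% |
| 10% | 7.3 | 50% | 45.0% | 52.3% |
| 20% | 14.6 | 50% | 40.0% | 54.6% |

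A simulation of 60,000 patients, with answers taken at Days 30, 91, 183, 365 and 730, agreed to within 0.2 points.

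A wider grid took 12-month patency of 40% to 80% and 12-month abandonment of 5% to 20%. At 24 months the estimate was 1.6 to 23.0 points lower (all lost) or 1.7 to 11.8 points higher (all patent) than under censoring.

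For scale, ignoring censoring, the 95% half-width with the target of 100 cases at 50% is 1.96 × √(0.5 × 0.5/100) = 9.8 points.

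**The case against.** A reader might infer that target-lesion patency has no stop for non-use at all. The documents do not support that. SAP 3.3.1 and 3.3.2 both end the period, as an event, when the patient leaves the study under 'Other', and the form's own label for that reason names non-use of the device. The gap is confined to patients who stay.

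A reader might also infer that a lost circuit alongside a patent lesion is an error in itself. It is partly what the protocol definitions imply. Section 9.1(1) looks only at the lesion, 9.1(4) ends at discontinuation of the circuit, and a circuit can fail elsewhere. On a purely anatomical view, later device status is legitimate. That view is weakened by the SAP, which already counts non-use as a target-lesion event in patients who leave.

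Other objections stand in part:

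- The case needs a patient who abandons the access without an earlier lesion event, remains in follow-up, and still receives a device answer or an occlusion report. If sites leave the question blank, the existing rule already comes close to censoring at abandonment. The form is not available to check.
- Parts of the SAP are masked, and a further rule could sit there. The masking inside the 3.3.1 and 3.3.2 tables looks like field names rather than missing rows.
- Censoring alone would be a poor remedy. It would censor patients who stay while the same table fails those who leave. It also assumes that abandonment is unrelated to impending lesion failure, which is doubtful when, for example, infection is the reason.

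**Conclusion.** The point holds in limited form. SAP 3.3.1 and 3.3.2 state no rule tied to the access-discontinuation date, and only study discontinuation coded 'Other' stops target-lesion patency for non-use. For patients who abandon the access event-free and stay, the result depends on later answers about an unused device, and the same abandonment gives different results by study status.

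The size cannot be established from the documents. The shifts of 2.5 to 10 points down and 1 to 5 points up rest on assumed 50% patency, 5% to 20% abandonment, independent constant hazards, and every answer going one way. They are extremes, and mixed answers would partly cancel. Reading them as a demonstrated bias would go too far. In the main illustration, only the all-lost extreme at 20% abandonment reaches the size of the sampling half-width, and at 5% the shift is small. Unlike sampling error, however, it would not shrink with more patients. Secondary target-lesion patency is exposed to the same gap but was not quantified.

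**What to change.** 1. Add the 3.3.3 clause to SAP 3.3.1 and 3.3.2: where an access-discontinuation date is entered, target-lesion events and 'Patency' dates are judged only up to that date, and later answers are ignored. An occlusion or target-lesion re-treatment on or before it remains an event for primary patency. For secondary patency the existing reversal rule applies up to the same date.
2. Choose one handling of abandonment with an open device, either censoring or event, and apply it both to patients who stay and to those who leave under 'Other'. If censoring is chosen, list the access-discontinuation date as a termination date and bring the existing 'Other' row into line. If event is chosen, add an access-discontinuation row.
3. Report the other option as a sensitivity analysis.

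The cost is a few lines of SAP text and a programming condition on a field already collected. Late follow-up becomes slightly shorter, so late intervals are slightly wider. Censoring would also bring the assumption that abandonment is unrelated to impending lesion failure, which the sensitivity analysis addresses.
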